- 3) Will use the Mass General Brigham Research Invitations procedures for recruitment. We will send prospective subjects a letter via the Research Invitation Program.

At the first point of contact (usually a phone call), a study co-investigator will provide a description of the study, discuss study procedure, and administer a phone screening questionnaire. Once the phone screening process is complete, the information gathered by the co-investigator will be taken to the PI of the study for further review. Once the PI agrees that the subject is thus far eligible, the subject will be scheduled their first visit. Consent form will be mailed to the subject ahead of time.

Informed consent will be obtained by a license physician, PI [name] [name] at SRH. The subject will meet with [name]. The test procedures will be described, and the testing equipment will be shown to the subject. [name] will clearly explain all the procedures and risks of the testing outlined in the consent form. The subject will be given an hour to consider their decision and will be encouraged to ask questions, both during the initial phone interview and throughout the study. [name] will answer any questions regarding the study at the time of the informed consent process. Once enrolled, the subject may pause or terminate his/her participation at any time during the study.

Participants will be randomized to receive active or sham RAVANS treatment 3 times per week for 2 weeks through a randomization approach with blocks of 4 (given the sample size of 48 participants, this would give 12 blocks of 4). Randomization of subjects will be blocked based on the 2 treatment options available.

V. STUDY PROCEDURES

First visit: consent, blood drawn, baseline evaluation, first RAVANS/Sham treatment

During this first visit, we will conduct the consent process. Participants that provide informed consent will be interviewed to complete inclusion/exclusion check list. The qualified subjects will be included in the study. They will complete the questionnaires (Demographic Data Questionnaire, Functional Comorbidity Index, Horowitz Lyme-MSIDS, Sedentary Behaviors Questionnaire, Fatigue Symptom Inventory, Brief Pain Inventory, Vulnerability questionnaire, Beck Depression Inventory, Beck Anxiety Inventory, Pittsburgh Sleep Quality Index), functional test (Timed Up and Go, 4 meter usually walking speed, NIH Toolbox cognitive battery), blood drawn and they will receive 1st RAVANS or sham treatment.

Blood test

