Subjects will receive RAVANS or sham treatment at clinic for 20 minutes. Subjects will complete the questionnaires (Horowitz Lyme-MSIDS, Sedentary Behaviors Questionnaire, Fatigue Symptom Inventory, Vulnerability Questionnaire, Brief Pain Inventory, Beck Depression Inventory, Beck Anxiety Inventory, Pittsburgh Sleep Quality Index), functional test (Timed Up and Go, 4 meter usually walking speed, NIH Toolbox cognitive battery), blood drawn for serum biomarkers (IL-6, IL-10, TNF, IL-1 β). Total visit times will be about 4 hours.

VI. BIOSTATISTICAL ANALYSIS

Our main outcome is to assess whether there is an improvement in symptoms (comparing before and after treatment) as indexed by HL-MSIDS score in the active RAVANS group as compared with sham. We chose the HL-MSIDS as the main outcome and therefore the other scale will be the secondary outcome. For the main analysis, we will compare the differences in HL-MSIDS changes between the two groups immediately after the end of treatment. We will therefore use an unpaired t-test for such analysis. Note here that we expect similar baseline level for both groups.

Besides this analysis, we will perform several exploratory analyses as listed below: we will compare the differences in changes in SBQ, FSI, BPI, BDI, BAI, PSQI, Timed- Up

and Go, 4m walk speed, NIHTB-CB, level of serum IL-6, IL-10, TNF, IL-1 β between the two groups immediately after the end of treatment. We will therefore use an unpaired t-test for such analysis.

Pearson correlation analysis will be applied to determine if serum level of biomarkers (IL-6, IL-10, TNF, IL-1 β) has correlation with symptom severity as index by HL-MSIDS, SBQ, FSI, BPI, BDI, BAI, PSQI, Timed- Up and Go, 4m walk speed, NIHTB-CB.

We will use the intention-to-treat analysis and do an analysis of only subjects that completed the 2-week study. For the intention-to-treat analysis, we will use a conservative method and assume that participants will not improve from the last measured point. The last-observation-carried-forward method will be appropriate because we expect no more than 10 percent of the observations were missing in each analysis.

Power analysis (e.g, sample size)

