Sample size was determined with reference to other studies that used similar endpoints. We assume that a standardized difference of 0.8 (the difference between groups divided by the standard deviation) is conservative to detect a clinically meaningful difference between groups (active RAVANS and sham). We will assume a type I error of 5% (alpha), a type 2 error of 10% (beta) and therefore the power will be 90%. Using the sample size calculation for a normal distributed population (t-test), 20 participants per arm will be necessary (total of 40 participants). Conservatively, we expect a 20% rate of dropout or loss to follow-up. We will assume that dropout participants will not improve from the last measured point; thus the sample size will be increased by 20% to 48 participants (24 per arm).

VII. RISK AND DISCOMFORTS

Blood Draws. Blood drawing may cause a small amount of pain. In addition, participants may get a temporary bruise or “black and blue mark”. Rarely, people faint when their blood is drawn. Very rarely, the vein may become red and swollen, or infected. If this occurs, we will treat the problem. Blood drawn will be performed by clinical phlebotomists to minimize the risk and discomforts.

Surveys/ Questionnaires. Some of the questions in the questionnaires may seem personal or embarrassing. Participants will be instructed that they may refuse to answer any of the questions that they do not wish to answer. If the questions make a participant very upset, we will help them to find a counselor. If participants develop fatigue during completing the questionnaire, we all ask the participant to take break.

RAVANS Risks: There is a small possibility of slight and temporary discomfort at the site where the electrodes are placed. Potential vaso-vagal reactions to stimulation

resulting in dizziness or light-headedness. The participant will be instructed to sit in chair while receiving RAVANS/Sham treatment.

The RAVANS procedure is without significant safety concerns. The electrical stimulator, checked by MGH Biomedical Engineering, has a current limiter preventing harmful stimulation levels.

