The proposed study will be monitored for safety, with monthly staff meetings reviewing adverse events and treatment outcomes and directly reporting any adverse events. The PI will also routinely monitor and assure the validity and integrity of collected data and adherence to the IRB approved protocol. The trained staff members who carry out the procedures will also carefully monitor the study throughout its duration. The team will evaluate the progress of the study, verify that the rights and well-being of the subjects are protected, verify that the reported study data are accurate, complete and verifiable from source documents, and that the conduct of the study is in compliance with the approved protocol and amendments.

We plan on performing interim data analysis with the first block of 12 subjects. Adverse events, data, and procedures will be reviewed by [name] and her team. If data are informative, we plan to publish the preliminary results. All expected and unexpected adverse outcomes will be reported to the IRB according to the Adverse Event Reporting guidelines.

X. REFERENCES

Aranow C, Atish-Fregoso Y, Lesser M, et al. Transcutaneous auricular vagus nerve stimulation reduces pain and fatigue in patients with systemic lupus erythematosus: a randomised, double-blind, sham-controlled pilot trial

Annals of the Rheumatic Diseases Published Online First: 03 November 2020. doi: 10.1136/annrheumdis-2020-217872

Capuron, L., & Miller, A. H. (2011). Immune system to brain signaling: neuropsychopharmacological implications. *Pharmacology & Therapeutics*, 130(2), 226–238. <https://doi.org/10.1016/j.pharmthera.2011.01.014>

Dantzer et al.; Dantzer, R., Konsman, J. P., Bluthé, R. M., & Kelley, K. W. (2000). Neural and humoral pathways of communication from the immune system to the brain: parallel or convergent? *Autonomic Neuroscience: Basic and Clinical*, 85(1-3), 60–65.

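### The primary t-test on HL-MSIDS change fixes the baseline slope at 1; ANCOVA on the baseline already collected would usually be more precise, by an amount the plan does not determine

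*Combined protocol and SAP*

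**What the plan says.** HL-MSIDS is the main outcome. The assessment table in Section V schedules it at Visit 1 and Visit 6 only, so each completer has one baseline and one post-treatment value.

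Section VI sets the primary contrast: "we will compare the differences in HL-MSIDS changes between the two groups immediately after the end of treatment". It then names the test and makes its only remark on baseline: "We will therefore use an unpaired t-test for such analysis. Note here that we expect similar baseline level for both groups". No baseline-adjusted model appears anywhere in the document.

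Two analysis sets are planned: "We will use the intention-to-treat analysis and do an analysis of only subjects that completed the 2-week study". In the intention-to-treat set, missing values are filled by last observation carried forward (LOCF).

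The power paragraph assumes "a standardized difference of 0.8 (the difference between groups divided by the standard deviation") with 5% type I error and 90% power. Section IV describes allocation in blocks of 4: "Randomization of subjects will be blocked based on the 2 treatment options available". It mentions no stratification by severity.

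**The concern.** A t-test on change is the same as modelling the Visit 6 score on treatment arm with the baseline coefficient set to exactly 1. If the true coefficient is lower, as regression to the mean usually makes it, the change score over-corrects for baseline and carries extra noise. ANCOVA estimates the coefficient and removes that noise.

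Expecting similar baselines does not settle the matter. Randomization balances baseline only on average, and ANCOVA gains precision whether or not an imbalance is seen.

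What is at stake is efficiency in a trial of 48. The planned test may use less of the information already collected than it could. The type I error and the unbiasedness of the planned test are not in question.

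**Working it through.** **Inputs from the plan.** 24 per arm, standardized difference 0.8, type I error 5% (sidedness not stated; taken as two-sided).

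**Assumed, because the plan is silent.** Correlation ρ between Visit 1 and Visit 6 of 0.3 to 0.95; ratio q of Visit 6 SD to baseline SD of 0.8 to 1.3; 0.8 read either in SDs of change or in SDs of the raw score.

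**The plan's own figure.** At 0.8, 5% and 90% power, a t-test needs 33 per arm two-sided (34 by exact t) or 27 one-sided (28 by exact t), not 20. The normal approximation gives 20 only for one-sided 5% and 80% power. The total of 48 is 40 × 1.2. That shortfall is a separate matter. Here it matters only because exact two-sided power at 24 per arm is 77.4%, which is the baseline for what follows.

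**Variance ratio.** In units of the baseline variance, the change score has variance 1 + q² − 2ρq per patient, and the ANCOVA residual has q²(1 − ρ²). Estimating the slope inflates the variance by about 1 + 1/(N − 4) = 1 + 1/44, or 2%. So

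ratio (ANCOVA / t-test) = q²(1 − ρ²) / (1 + q² − 2ρq) × (1 + 1/44).

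For q = 1 the first factor is (1 + ρ)/2. At ρ = 0.5 the ratio is 0.75 × 1.0227 = 0.767, and 24 / 0.767 = 31.3 patients per arm under the t-test would give the same variance.

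**Power with no dropout and q = 1** (simulation, 40,000 trials per scenario), t-test vs ANCOVA:

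| ρ | Variance ratio | Equivalent n per arm | 0.8 in change SDs | 0.8 in raw-score SDs |
|---|---|---|---|---|
| 0.3 | 0.665 | 36.1 | 78 vs 91% | 63 vs 80% |
| 0.5 | 0.767 | 31.3 | 78 vs 87% | 77 vs 87% |
| 0.7 | 0.869 | 27.6 | 78 vs 83% | 94 vs 96% |
| 0.9 | 0.972 | 24.7 | 77 vs 79% | 100 vs 100% |

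At ρ = 0.95 the ratio is 0.997, and power in change SDs is 77% for both.

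**Unequal SDs (0.8 in change SDs).** With q = 0.8 and ρ from 0.5 to 0.9, power is 77–78% vs 92–95%. With q = 1.3 it is 77.8 vs 80.4% at ρ = 0.5, 77.4 vs 76.8% at 0.7 and 77.4 vs 76.7% at 0.8. With q = 1.1 and ρ = 0.9 it is 77.4 vs 76.4%. The true slope is ρq. The losses occur at 1.3 × 0.7 = 0.91, 1.3 × 0.8 = 1.04 and 1.1 × 0.9 = 0.99, all near 1.

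**The two planned data sets.** Section VI gives two missing-data rates: "we expect no more than 10 percent of the observations were missing in each analysis" and "Conservatively, we expect a 20% rate of dropout or loss to follow-up". For 24 per arm these are 2.4 and 4.8, taken as 2 and 5 missing. With no HL-MSIDS between Visits 1 and 6, LOCF sets a dropout's change to 0. Assuming dropout is random and equal in both arms, q = 1 and 0.8 in change SDs, power (t-test vs ANCOVA) is:

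| Missing per arm | Data set | ρ = 0.5 | ρ = 0.7 | ρ = 0.9 |
|---|---|---|---|---|
| 2 | LOCF | 73 vs 82% | 73 vs 78% | 73 vs 74% |
| 2 | Completers | 74 vs 84% | 73 vs 79% | 74 vs 75% |
| 5 | LOCF | 65 vs 74% | 66 vs 70% | 66 vs 66% |
| 5 | Completers | 67 vs 78% | 67 vs 73% | 67 vs 68% |

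Under these assumptions the type I error was 4.8 to 5.2% for both tests.

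**Chance imbalance.** The baseline difference has SE √(2/24) = 0.289 SD. It exceeds 0.3 SD in 30% of trials and 0.5 SD in 8%. With q = 1, a 0.3 SD imbalance shifts the change-score estimate by (1 − ρ) × 0.3 = 0.21, 0.15, 0.09 or 0.03 baseline SD at ρ = 0.3, 0.5, 0.7 or 0.9. In change SDs the effect is 0.8 × √(2(1 − ρ)) = 0.95, 0.80, 0.62 or 0.36 baseline SD, so the shift is 22%, 19%, 15% or 8% of it. In raw-score SDs the effect is 0.80, and the shift is 26%, 19%, 11% or 4%. The shift is equally likely in either direction.

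**The case against.** The strongest reply is that nothing in the plan is wrong. The test is valid, baseline is already subtracted, and this is an exploratory pilot. Visits 1 and 6 are about two weeks apart in a chronic condition, so the correlation may well be high, and at 0.9 or above the gain is at most about 1 point with equal SDs. This stands as a limit on size. It does not support fixing the slope at 1, since the plan gives no figure that would justify that value.

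A second point also has force. LOCF places every dropout exactly on a slope of 1, and the LOCF figures above assume random dropout. If the 5 dropouts per arm tend to have worse baselines (selected on baseline plus noise of equal variance), power at ρ = 0.5 is 68 vs 72% rather than 65 vs 74%. If both arms also improve by 0.5 change SD, it is 64 vs 65% at ρ = 0.5 and 63 vs 62% at ρ = 0.7. The loss reaches about 1.3 points when the common improvement is 1 SD. So in the intention-to-treat set the gain can vanish even at moderate correlation.

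Third, the imbalance shifts are already part of the t-test's standard error and hence of its power. They describe what can happen in a single trial and are not an additional cost. Finally, a t-test on change makes change SDs the more natural reading of 0.8, so the raw-score column carries less weight.

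**Conclusion.** The concern holds as a recommended efficiency improvement; it does not correct a biased or invalid test. ANCOVA would usually be more precise than the planned t-test, by an amount the plan's inputs do not determine. Over the main scenarios, power changes by between about +17 points and −1 point. The largest gains need either a Visit 6 SD 20% below baseline or a low correlation with 0.8 in raw-score SDs. The losses occur where the slope is close to 1, a situation that severity-related dropout under LOCF makes more likely. All of these figures rest on assumed correlations, SD ratios and dropout patterns. The case for change is this asymmetry: the possible loss is small and the possible gain is not. ANCOVA should not be presented as a remedy for the sample-size shortfall or for LOCF.

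**What to change.** In Section VI, make the primary analysis an ANCOVA of Visit 6 HL-MSIDS on treatment arm and baseline HL-MSIDS, reporting the adjusted mean difference with its 95% CI. Apply it to the same intention-to-treat (LOCF) and completer sets as now planned. In the power paragraph, align the reference to the t-test and state whether 0.8 is in SDs of change or of the raw score. The exploratory outcomes may use the same model, each with its own baseline.

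Timing matters. Section IX says: "We plan on performing interim data analysis with the first block of 12 subjects". It does not say whether that look is unblinded, so the change should be fixed before any unblinded look. If unblinded outcome data have already been seen, keep the t-test as primary and report the ANCOVA as supportive, labelled as added later.

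The cost is a few sentences of analysis text and an amendment to the IRB-approved protocol, with no new data, visits or patients. The statistical price is one degree of freedom and about 2% variance inflation, which means a loss of about 1 point of power when the slope is close to 1.

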Increasing evidence shows that transcutaneous auricular nerve stimulation (taVNS) can significantly reduce multiple symptoms of stress disorder including depression, fatigue, cognitive impairment, anxiety, psychomotor retardation, sleep disturbance (Kong et al, 2018; Aranow et al 2020). One of the collaborators in this study [name] has developed and patented RAVANS, a type of taVNS, which synchronizes stimulation to the respiratory cycle, modulate vagal systems and optimize stimulations (Napadow et al 2012; Garcia et al, 2017; Yakunina et al 2017). RAVANS has been shown beneficial effect in pain management (Napadow et al 2012; Garcia et al, 2017).

In this study, we will conduct a randomized, double blinded, sham-controlled pilot study to **explore the effect of RAVANS on the symptoms in individuals diagnosed with PTLDS using psychometric measurement, function and cognitive test, and serum biomarkers.**

II. SPECIFIC AIMS

Aim 1. Determine if Respiratory-gated Auricular Vagal Afferent Nerve Stimulation (RAVANS) can improve symptoms of Post-Treatment Lyme Disease Syndrome (PTLDS)

Aim 2: Determine if RAVANS reduces inflammation as measured by serum biomarkers (IL6, IL-10, TNF, IL-1 β) after RAVANS treatment in people with PTLDS

Aim3: Determine if inflammation as measured by serum biomarkers (IL-6, IL-10, TNF, IL-1 β) correlates with severity of PTLDS.

INVESTIGATORS:

[name] [name], PhD, Spaulding Rehabilitation Hospital

Principal Investigator, recruitment, screening and consenting, data collection and analysis

[name], Spaulding Rehabilitation Hospital

*Medical Monitor

[name], Massachusetts General Hospital

Co-investigator, recruitment, data analysis

[name], LicAc, Massachusetts General Hospital

Co-investigator, RAVANS inventor, RAVANS technical support, data analysis,

*Responsibilities of the Medical Monitor

The medical monitor is required to review all unanticipated problems involving risk to subjects or others, serious adverse events and all subject deaths associated with the protocol and provide an unbiased written report of the event. At a minimum, the medical monitor must comment on the outcomes of the event or problem and in case of a serious adverse event or death, comment on the relationship to participation in the study. The medical monitor must also indicate whether he concurs with the details of the report provided by the principal investigator.

III. SUBJECT SELECTION

Inclusion criteria include:

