Fifteen mL of venous blood will be collected by vein for future measurement of serum biomarkers (IL-6, IL10, TNF, IL-1 β).

Questionnaires/ Surveys. A standard demographic survey and PTLDS symptoms will be collected using questionnaires outlined below.

1. Demographic Data Questionnaire (DDQ). A standard survey will be used to collect data including age, gender, racial background, marital status, education, employment and occupation, income.
2. Functional Comorbidity Index (FCI). Presence of chronic medical conditions will be measured using FCI which is a validated and reliable self-administered 18-item scale designed to examine the impact of comorbidities on physical function. Each participant will be asked to provide a list of prescription, over the counter, and recreational drugs used in the past 7 days.
3. Horowitz Lyme-Multiple Systemic Infectious Diseases Syndrome (HL-MSIDS) Questionnaire: This 55-item questionnaire evaluates the frequency, severity, and incidence of Lyme symptoms as well as assessing one's perceived overall health. A Likert scale from 0 - 3 (none – severe) is used to assess symptom frequency. The subsequent section assigns points to certain symptoms based on the answers in the first section. The third and fourth sections ask the subject to assign points to symptom incidence and health perception.
4. Sedentary Behaviors Questionnaire (SBQ): This 18-item questionnaire asks about the amount of time spent engaged in sedentary behaviors on typical weekdays and weekends.
5. Fatigue Symptom Inventory (FSI): This non-diagnosis-specific questionnaire measures the severity of fatigue symptoms and how much these factors interfere with the subjects' lives. There are 14 items, most of which are 0-10 point scales, one question asking about the amount of days fatigue is present, and another is a 0-4 scale on severity of fatigue. The higher the overall score correlates with more severe fatigue symptoms.
6. Brief Pain Inventory (BPI): This 15-item questionnaire assesses the location, severity, and type of current pain, using analogue scales and body diagrams.
7. Vulnerability questionnaire (VQ) This is a medical history questionnaire to ask about possible vulnerabilities to long-term neuroinflammation. Example questions include asking about the extent of previous use of antibiotics, opioids, anti-inflammatory steroids (e.g., prednisone), and previous exposure to pollutants and toxins.

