8. Beck Depression Inventory (BDI): This questionnaire evaluates current depressive symptoms. There are 21 items, each having four possible answers. Each item is scored between 0 and 3, with a higher score indicating greater symptom severity. The different items cover both psychological (e.g. concentration) and physical (e.g. appetite) symptoms of depression.

9. Beck Anxiety Inventory (BAI): This questionnaire evaluates current anxiety symptoms. There are 21 items, each having four possible answers. Each item is scored between 0 and 3, with a higher score indicating greater symptom severity. The different items cover both psychological (e.g. nervousness) and physical (e.g. hands trembling) symptoms of anxiety.
10. Pittsburgh Sleep Quality Index (PSQI): This 9-item questionnaire assesses sleep quality and patterns of sleep in adults over the past 30 days. It covers subjective sleep quality, latency, duration, habitual sleep efficiency, disturbances, use of sleeping medications, and daytime dysfunction due to poor sleep.

Objective Functional Tests. Participants will be asked to perform two functional tests; the Timed Up and Go (TUG) and the 4m usual walk speed. The Timed Up and Go test, and usual walk speed are commonly used objective tests of physical function, that independently predict poor outcomes in older adults. Minimal clinically important differences are 0.1 meters per second for gait speed, whereas a chair stand time of \geq 12 seconds predicts a 2.4-fold increased risk of falls in older adults.

Objectively measured Cognitive Function. We will use the NIH Toolbox Cognition Battery (NIHTB-CB) to assess cognitive function in participants with PTLDS. The NIHTB-CB is a computerized adaptive test that assesses several cognitive domains. It is administered by iPAD using the NIH Toolbox™ iPAD app. The following cognitive domains are assessed: executive function (inhibitory control/attention: Flanker Task; cognitive flexibility: Dimensional Change Card Sort), working memory (List Sorting), short-term memory (Picture Sequence), and an overall composite score that combines these outcomes (Fluid Cognition Composite).

Intervention:

RAVANS Procedures

The participant will be treated with RAVANS or sham at clinic for 20 minutes 3 times per week for 2 weeks.

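### Aim 3 rests on unadjusted Pearson correlations although age, gender and comorbidity are collected; an adjusted coefficient beside each raw one would be a cheap improvement to an exploratory aim

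*Combined protocol and SAP*

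**What the plan says.** Section II sets the third aim: "Determine if inflammation as measured by serum biomarkers (IL-6, IL-10, TNF, IL-1 β) correlates with severity of PTLDS". Section VI answers it in a single sentence: "Pearson correlation analysis will be applied to determine if serum level of biomarkers" (the four cytokines) "has correlation with symptom severity as index by HL-MSIDS, SBQ, FSI, BPI, BDI, BAI, PSQI, Timed- Up and Go, 4m walk speed, NIHTB-CB". No covariate, partial correlation, regression or stratification is named for this or any other analysis. The sentence does not say whether the values come from Visit 1, Visit 6, both, or the change between them. It follows a list that Section VI introduces as exploratory.

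Section V collects the obvious adjustment variables. For the demographic questionnaire: "A standard survey will be used to collect data including age, gender, racial background". For comorbidity: "Presence of chronic medical conditions will be measured using FCI", a self-administered 18-item scale "designed to examine the impact of comorbidities on physical function". The assessment schedule places both at Visit 1, and neither appears in Section VI. Section V describes Timed Up and Go and usual walk speed as tests of physical function "that independently predict poor outcomes in older adults"; Section VI then uses both as indices of symptom severity.

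Section III admits adults from 18 with no upper age limit. It excludes current acute illness or infection, neurological disorders judged to interfere, some psychiatric illness, and steroid or immunosuppressant use. It does not exclude chronic non-neurological conditions as such.

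**The concern.** Aim 3 is an association across participants, not a comparison of arms, so randomization does not balance third factors that may drive both variables. If older or more comorbid participants have higher cytokine levels and also walk more slowly, a raw correlation appears even when inflammation has no link to PTLDS. The trial could then report that a cytokine tracks PTLDS severity when it has shown only that both vary with age or general health.

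The document's own wording supports this most directly for Timed Up and Go and walk speed, because it ties comorbidity to physical function and discusses these tests by reference to older adults. That is 2 measures × 4 cytokines = 8 of the 10 × 4 = 40 planned pairs, counting the NIH Toolbox battery as one measure. What is at stake is the interpretation of an exploratory aim.

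**Working it through.** The plan gives no power, precision or error-rate figure for Aim 3, so there is nothing of its own to reproduce. I use the sample sizes in Section VI as given: 40 participants before allowance for dropout and 48 after it.

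**Assumptions (none in the documents).** One factor, such as age or comorbidity, correlates a with the cytokine and a with the severity measure. There is no direct link between the two, the data are normal, and the test is two-sided at 5%.

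**Step 1, induced correlation.** The raw correlation is centred on a × a. For a = 0.5 this is 0.25.

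**Step 2, rejection threshold.** With k covariates, df = n − 2 − k and critical |r| = t / √(t² + df). For n = 48 and k = 0, df = 46 and critical |r| = 0.285. For n = 40 it is 0.312.

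**Step 3, false-positive rate per test**, from 40,000 simulated samples per row and sample size. The partial correlation adjusts for the confounder:

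| a | induced r | raw, n = 48 | raw, n = 40 | partial, n = 48 | partial, n = 40 |
|---|---|---|---|---|---|
| 0.2 | 0.04 | 6.0% | 5.7% | 5.1% | 4.9% |
| 0.3 | 0.09 | 9.4% | 8.5% | 5.0% | 5.0% |
| 0.4 | 0.16 | 19.0% | 16.6% | 5.0% | 5.2% |
| 0.5 | 0.25 | 40.9% | 34.6% | 5.0% | 4.9% |

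Fisher-z check for a = 0.5, n = 48: atanh(0.25) × √45 = 0.2554 × 6.708 = 1.713, and 1 − Φ(1.960 − 1.713) = 1 − Φ(0.247) ≈ 40%, in line with the simulation. Unequal links fall between the rows: 0.3 × 0.4 = 0.12 gives about 13% at n = 48, and 0.4 × 0.5 = 0.20 gives about 28%.

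**Step 4, cost of adjusting for age, gender and FCI count (k = 3).** Critical |r| moves from 0.285 to 0.294 at n = 48, and from 0.312 to 0.325 at n = 40. Approximate power is 1 − Φ(1.960 − atanh(r) × √(n − 3 − k)). For a partial r of 0.4, atanh(0.4) = 0.4236:
- n = 48, unadjusted: 0.4236 × √45 = 2.842, power 81%.
- n = 48, adjusted: 0.4236 × √42 = 2.745, power 78%.
- n = 40: power falls from 73% to 70%.

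**The case against.** The strongest defence is that this is a pilot, that the correlations sit among the exploratory analyses, and that Aim 3 asks only whether biomarkers correlate with severity. A Pearson coefficient answers that question as worded and makes no causal claim. This stands. It is why the raw coefficient should stay and why the point is an improvement, not a flaw in the main analysis. It does not remove the difficulty that a slow walk due to age or another chronic condition is not PTLDS severity, which is what the aim names.

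Three stronger readings are tempting, and the documents support none of them.

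- A reader might infer that other inflammatory or disabling illness is kept out only through the drug exclusions. Section III excludes acute illness or infection, interfering neurological disorders and some psychiatric illness whatever the medication. Section I also calls PTLDS a diagnosis of exclusion. These criteria narrow the scope for confounding by comorbidity but do not close it.
- A reader might infer that all ten severity measures are shown to depend on age or comorbidity. The documents make that link only for physical function. They say nothing of the kind for HL-MSIDS, the other questionnaires or the NIH Toolbox battery, and do not say whether the battery's scores are age-corrected.
- A reader might infer that a large false-positive rate has been demonstrated. No correlation of age or comorbidity with cytokines or severity is given, and with links of 0.2 to 0.3 the inflation is small.

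Two further objections also stand. The return to about 5% assumes the confounder is measured without error, whereas the FCI is self-administered. The right covariates also depend on the visit analysed: at Visit 6, treatment arm could itself link cytokines and severity, while with change scores stable differences in age and comorbidity would be expected to matter less.

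**Conclusion.** The point holds as a cheap improvement to an exploratory aim. The plan collects age, gender and comorbidity, tests an observational association without them, and leaves the visit unstated. For the functional tests in particular, a raw correlation could not be read as evidence about PTLDS severity.

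The size of the bias is unknown from the documents. At n = 48 the per-test false-positive rate runs from about 6% to about 41% as the assumed links run from 0.2 to 0.5. The calculation rests on a single confounder, equal links, normal data and no direct effect. The HL-MSIDS comparison, the other between-arm comparisons and the sample size are unaffected.

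**What to change.** In Section VI:

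1. State that Aim 3 uses Visit 1 values, taken before the first treatment.
2. Beside each raw Pearson coefficient, report a prespecified partial correlation, or a linear regression of the severity measure on the cytokine, adjusted for age, gender and FCI count.
3. If Visit 6 values are also analysed, add treatment arm as a covariate.
4. Describe an association as related to PTLDS severity only if it persists after adjustment, and say in advance what counts as persisting.

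Fix the covariates before any results are seen. The change takes a few sentences and no new data. It costs three degrees of freedom (df from 46 to 43 at n = 48) and about 3 points of power for a partial r of 0.4. Some confounding will remain because the FCI is self-reported, and the write-up should say so.
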